This document is confidential and the property of Stanford University School of Medicine.

8.3.1	Study Sponsor Notification by Investigator	11
8.3.2	EC/IRB Notification by Investigator	12
8.3.3	FDA Notification by Sponsor	12
8.4	UNBLINDING PROCEDURES.....	12
8.5	STOPPING RULES	ERROR! BOOKMARK NOT DEFINED.
8.6	MEDICAL MONITORING.....	12
8.6.1	Internal Data and Safety Monitoring Board	Error! Bookmark not defined.
8.6.2	Independent Data and Safety Monitoring Board	Error! Bookmark not defined.
9	DATA HANDLING AND RECORD KEEPING	12
9.1	CONFIDENTIALITY	12
9.2	SOURCE DOCUMENTS.....	13
9.3	CASE REPORT FORMS.....	13
9.4	RECORDS RETENTION.....	13
10	STUDY MONITORING, AUDITING, AND INSPECTING	13
10.1	STUDY MONITORING PLAN	13
10.2	AUDITING AND INSPECTING.....	14
11	ETHICAL CONSIDERATIONS	14
12	STUDY FINANCES	14
12.1	FUNDING SOURCE	14
12.2	CONFLICT OF INTEREST	15
12.3	SUBJECT STIPENDS OR PAYMENTS	ERROR! BOOKMARK NOT DEFINED.
13	PUBLICATION PLAN	15
14	REFERENCES	15
15	ATTACHMENTS	15

CONFIDENTIAL

This document is confidential and the property of Stanford University School of Medicine.

List of Abbreviations

ESQ – Esophageal symptoms questionnaire

NMDA - N-methyl-D-aspartate

POEM - Peroral endoscopic myotomy

SHC – Stanford Hospital & Clinics

CONFIDENTIAL

This document is confidential and the property of Stanford University School of Medicine.

Study Summary

Title	A prospective, randomized, double-blind, placebo-controlled trial of the effects of magnesium sulfate on postoperative esophageal spasm-associated pain following peroral endoscopic myotomy
Short Title	MgPOEM
Protocol Number	58859
Methodology	Randomized, double-blind, placebo-controlled prospective trial
Study Duration	2 years
Study Center(s)	Single-center
Objectives	This study hypothesizes that among patients having peroral endoscopic myotomy, intraoperative magnesium sulfate infusion will reduce the severity of postoperative pain while decreasing perioperative opioid requirements.
Number of Subjects	100
Diagnosis and Main Inclusion Criteria	Diagnosis: Esophageal motility disorder, including achalasia Main Inclusion Criteria: Patient undergoing peroral endoscopic myotomy
Study Product, Dose, Route, Regimen	Magnesium sulfate. 50 mg/kg (based on lean body weight) intravenous over 15 minutes at start of mucosal incision, followed by 25 mg/kg/hr infusion that is turned off at patient extubation
Duration of administration	Only limited to surgery duration, from start of mucosal incision to patient extubation
Reference therapy	Reference is placebo (normal saline)
Statistical Methodology	Chi-square test to compare primary outcome (postoperative pain) Chi-square test, Fisher's exact test, or Mann-Whitney U test to compare secondary outcomes (intraoperative opioid usage, postoperative opioid usage, pain at 24 hours, esophageal symptoms questionnaire results)

CONFIDENTIAL

This document is confidential and the property of Stanford University School of Medicine.

1 Introduction

This document is a protocol for a human research study. This study is to be conducted according to US and international standards of Good Clinical Practice (FDA Title 21 part 312 and International Conference on Harmonization guidelines), applicable government regulations and Institutional research policies and procedures.

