1.5 Dose Rationale and Risk/Benefits

The magnesium bolus dosing of 50 mg/kg emulates the dose used in a recent urologic study that explored the effect of magnesium to decrease bladder catheter-associated discomfort.⁹ Furthermore, this bolus dose and the infusion rate are the most frequently reported dose/rate in a meta-analysis of 20 randomized controlled trials.¹² The aforementioned meta-analysis found no major adverse events associated with magnesium toxicity, whilst finding a statistically and clinically significant decrease in postoperative pain. The medication is administered intravenously as part of the intraoperative anesthetic regimen. The POEM surgery lasts on average 1 to 2 hours, which is the maximum duration of the magnesium infusion. This will limit the risk of magnesium toxicity. Hence, the study will be safely investigating a nonopioid analgesic that has been shown to be efficacious in similar populations undergoing a diverse range of surgeries, with the hope of clarifying the antispasmodic potential of magnesium.

2 Study Objectives

Primary Objective

To assess the efficacy of magnesium sulfate on decreasing esophageal spasm-associated pain as measured by subjective pain scores and the esophageal symptoms questionnaire score.¹⁴

Secondary Objective

To assess the efficacy of magnesium sulfate on decreasing intraoperative opioid usage.
 To assess the efficacy of magnesium sulfate on decreasing postoperative opioid consumption.
 To assess the efficacy of magnesium sulfate on decreasing discharge opioid prescription.
 To assess the efficacy of magnesium sulfate on decreasing postoperative pain as measured by the esophageal symptoms questionnaire score at 24 hours.

3 Study Design

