3.3 Secondary Study Endpoints

This study will assess the efficacy of magnesium sulfate on decreasing intraoperative opioid usage, postoperative opioid consumption, discharge opioid prescription, and on decreasing postoperative pain as measured by the esophageal symptoms questionnaire score at 24 hours.

4 Subject Selection and Withdrawal

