6.2 Day of surgery

- 6.2.1 In the preoperative holding area, all enrolled patients will have preoperative plasma calcium and magnesium levels drawn and complete the esophageal symptoms questionnaire (ESQ), a validated survey to assess symptoms of dysphagia, globus, and reflux.

6.2.2 The patient will proceed to the OR for anesthetic care.

- 6.2.2.1 Patients will undergo rapid sequence induction of general anesthesia. In the control group, the anesthesia team will use ketamine, propofol, succinylcholine, and esmolol and/or opioids at their discretion. In the treatment arm, the anesthesia team will use ketamine and propofol using lean body weight (LBW) dosing, and succinylcholine at total body weight (TBW) dosing. After endotracheal tube placement and confirmation, sevoflurane in air and oxygen will be used for maintenance of general anesthesia. The anesthesiologist will ensure adequate neuromuscular relaxation throughout the case.

- 6.2.2.2 In the treatment arm, the anesthesia team will prepare a magnesium sulfate infusion within a 20 ml syringe. Patients will receive a magnesium sulfate bolus of 50 mg/kg lean body weight over 15 minutes, followed by a magnesium sulfate infusion at 25 mg/kg/hr when the endoscopist begins mucosal incision. In addition, the patients will receive dexamethasone 0.1-0.2 mg/kg at the start of case, and ondansetron 4 mg at the end of case. The magnesium infusion will be discontinued at extubation. After surgery, patients will be admitted to the postanesthesia care unit. For mild pain reported as a numeric score ranging from 1 to 3, acetaminophen 1000 mg IV will be offered. For pain greater than a score of 3, opioids (fentanyl and hydromorphone) will be available. For nausea and vomiting, prochlorperazine and haloperidol will be provided. Calcium gluconate and a code cart with emergency drugs and airway equipment will be made available in case of symptoms concerning for magnesium toxicity.

- 6.2.2.3 In the control arm, the anesthesia team will prepare a normal saline infusion within a 20 ml syringe. Patients will receive a normal saline bolus of 50 mg/kg lean body weight over 15 minutes, followed by a normal saline infusion at 25 mg/kg/hr when the endoscopist begins mucosal incision. Opioids (fentanyl and hydromorphone) will be administered for analgesia at the discretion of the anesthesia team. In addition, patients

CONFIDENTIAL

This document is confidential and the property of Stanford University School of Medicine.

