7.2 Statistical Methods

Data will be expressed as means \pm SD, number (proportion), relative risk, 95% CI, absolute risk reduction, or number needed to treat.

The primary outcome is the incidence of esophageal spasm-related pain at 0 h postoperatively, compared using the chi-square test.

The secondary outcomes of the incidence of esophageal spasm-related pain at 24 hours postoperatively, intraoperative opioid usage, postoperative opioid consumption, and discharge opioid prescription will be compared using the chi-square test or Fisher's exact test as appropriate. Continuous variables will be compared using the Mann–Whitney *U* test. Categorical variables will be compared using the chi-square test or Fisher's exact test as appropriate.

Post hoc subgroup analyses will be conducted regarding the incidence of esophageal spasm-related pain according to achalasia type (e.g. type 1, 2, or 3), preoperative H2-receptor antagonist use, preoperative proton pump inhibitor use, and intraoperative opioid usage. *Post hoc* subgroup analysis will be further conducted on postoperative magnesium levels and the incidence of esophageal spasm-related pain at 24 hours.

All *P* values will be two-sided, and a value of $P < 0.05$ will be considered statistically significant.

Comparisons of postoperative pain between the two groups at time 0 h and time 24 h will be analyzed using the Mann–Whitney *U* test and performed using an adjusted significance level of 0.0125 (0.05/4) after *post hoc* analysis using the Bonferroni method.

Statistical analyses will be performed using R version 4.0.3.

CONFIDENTIAL

This document is confidential and the property of Stanford University School of Medicine.

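### The stated hypothesis is lower perioperative opioid requirements, but no endpoint combines intraoperative and postoperative opioid, and no rule covers the case where the two phases disagree

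*Combined protocol and SAP*

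**What the plan says.** The Study Summary's objective is that "intraoperative magnesium sulfate infusion will reduce the severity of postoperative pain while decreasing perioperative opioid requirements". Its statistical row then lists the secondary outcomes as "intraoperative opioid usage, postoperative opioid usage, pain at 24 hours, esophageal symptoms questionnaire results".

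Section 2 makes intraoperative usage, postoperative consumption and discharge prescription three separate objectives. Section 3.3 repeats the split: "decreasing intraoperative opioid usage, postoperative opioid consumption, discharge opioid prescription". In Section 7.2, "intraoperative opioid usage, postoperative opioid consumption, and discharge opioid prescription will be compared using the chi-square test" or Fisher's test as appropriate. A later sentence assigns Mann–Whitney U to continuous variables, without saying whether opioid use is one of them. P values are judged two-sided at 0.05.

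No section defines a combined amount, a common unit for fentanyl and hydromorphone, a time window for postoperative opioid, or how the opioid results are to be read together.

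The opioid text also differs by arm:

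- **During surgery.** Sections 6.2.2.1 and 6.2.2.3 leave opioids to the anesthesia team's discretion in the control arm. Sections 6.2.2.1 and 6.2.2.2 name no intraoperative opioid for the magnesium arm, yet Section 5.6 expects narcotics as part of standard care without distinguishing the arms.
- **In recovery.** For the magnesium arm, Section 6.2.2.2 says: "For pain greater than a score of 3, opioids (fentanyl and hydromorphone) will be available". For the control arm, Section 6.2.2.3 makes the same drugs available and gives no score threshold.
- **Blinding.** Section 5.8 blinds the endoscopist and the patient. Under Section 5.4 the anesthesia team prepares the syringe from the envelope instructions.

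**The concern.** The two phases can substitute for each other. Opioid withheld during surgery can be given in recovery, where both arms have fentanyl and hydromorphone. A lower intraoperative amount therefore does not by itself show that the patient needed less opioid.

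The intraoperative endpoint is also the one most open to influence, because a team that knows the allocation decides the amount. If the phases point in different directions, the plan does not say whether the opioid half of its hypothesis is supported. A report could rest the claim on whichever phase was favourable.

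**Working it through.** **1. What the plan gives.** There is no power or sample-size figure for any opioid endpoint, so there is none to reproduce. The only sample size is for the primary outcome: 45 per group, and 45/0.9 = 50 after 10% dropout. I use 45 per arm below. The documents give no opioid mean, SD or phase split, so every other input here is an assumption.

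**2. Why the postoperative test is the weaker of the two.** Suppose half of the control total is given intraoperatively and the totals are equal.

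- Magnesium-arm share 40%: the intraoperative ratio is 0.40/0.50 = 0.80 and the postoperative ratio is 0.60/0.50 = 1.20.
- Magnesium-arm share 30%: the ratios are 0.30/0.50 = 0.60 and 0.70/0.50 = 1.40.

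The same amount leaves one phase and enters the other, but the proportional fall is larger than the proportional rise: 1/0.80 = 1.25 against 1.20, and 1/0.60 = 1.67 against 1.40.

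**3. Simulation on amounts, equal true totals.** Patient totals are lognormal with a coefficient of variation of 0.5 to 1.0. The intraoperative share follows a Beta distribution with concentration 10, with a mean of 50% in control and 40% or 30% in magnesium. Intraoperative amount = total × share; postoperative amount = total × (1 − share). The test is Mann–Whitney, two-sided 0.05, with at least 1,000 runs per scenario. Repeat runs move the figures by a few percentage points.

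| Result, % of trials | 40% share | 30% share |
|---|---|---|
| Significant intraoperative decrease | 23–47 | 78–99 |
| Significant postoperative increase | 18–36 | 48–88 |
| Intraoperative decrease without significant postoperative increase | 23–34 | 15–49 |
| Significant decrease in the total | 2–3 | 2–3 |

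The last row is what a two-sided 0.05 test gives by design in one direction: 0.05/2 = 2.5%.

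**4. A second model.** Here the phases are independent lognormal amounts with equal means, and a fraction of the magnesium arm's intraoperative opioid is moved to recovery. Moving 25% gives a significant intraoperative decrease in 61% of runs, a significant postoperative increase in 64%, and a decrease in the total in 3%. Moving 50% gives 99.9%, 98% and 3%. In this model the postoperative endpoint exposes the shift about as often as the intraoperative endpoint is misled by it.

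**5. If opioid use is analysed as yes/no.** Power = Φ[(|p1 − p2|√n − 1.96√(2p̄(1 − p̄))) / √(p1(1 − p1) + p2(1 − p2))], with n = 45 and assumed rates.

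- Intraoperative fall, 90% to 50%: (2.683 − 1.96 × 0.648)/0.583 = 2.42, so power is 99%.
- Postoperative rise, 60% to 70%: (0.671 − 1.96 × 0.675)/0.671 = −0.97, so power is 17%.
- Postoperative rise, 60% to 80%: (1.342 − 1.96 × 0.648)/0.632 = 0.11, so power is 54.5%.

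A chi-square analysis can therefore register the intraoperative fall almost every time and usually miss a modest rise in recovery.

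**6. A true saving.** With a 30% reduction in the total and a 40% share, the ratios are intraoperative 0.70 × 0.40/0.50 = 0.56, postoperative 0.70 × 0.60/0.50 = 0.84, and total 0.70. Under the model of step 3, a significant decrease appears in 84–99% of trials intraoperatively, 13–26% postoperatively and 47–92% on the total.

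**The case against.** The strongest reply is that postoperative consumption is itself a named objective and endpoint, so opioid moved to recovery should appear there as an increase. That stands in part. A reader might infer that the plan would simply count shifted opioid as a reduction. The documents do not support this: it counts as a reduction only on the intraoperative endpoint, and steps 3 and 4 show that the postoperative test often reveals the shift. It is not a dependable safeguard, because it fails in a material share of trials, is weaker on a yes/no analysis, and has no interpretation rule attached.

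A reader might also infer that the trial would miss a real saving. Step 6 does not support that: the intraoperative test is significant more often than the total. The difficulty is that the same test also responds to pure shifting, so its result cannot separate the two.

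Three further replies have force. The word perioperative is not defined and may mean only that both phases are of interest, so reading it as a sum is an interpretation. Separate phases answer separate clinical questions, so reducing them to descriptive status would be a trade-off rather than a correction. Finally, a summed endpoint inherits any bias from the unblinded anesthesia team and the arm-specific opioid text.

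**Conclusion.** The gap is real. The opioid half of the hypothesis has no endpoint that combines the phases, and the plan does not say what to conclude when they disagree. Under the assumptions of step 3, with no true saving, about 15–49% of trials show an intraoperative decrease that the postoperative test does not contradict at 0.05, against about 2–3% showing a false decrease on the total. These figures illustrate a mechanism and do not predict this trial; they depend on the assumed spread, shares and degree of substitution.

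The point concerns secondary endpoints only; the primary comparison of pain incidence at 0 h and its sample size are untouched. It should be settled before analysis because it decides whether an overall opioid-sparing claim can be made. It does not follow that a total would make that claim unbiased.

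**What to change.** In Sections 3.3 and 7.2:

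1. Add total perioperative opioid as a secondary endpoint: intraoperative plus postoperative opioid up to the POD1 assessment, one amount per patient, in morphine equivalents by one fixed conversion table, compared with Mann–Whitney U.
2. Keep intraoperative and postoperative opioid as reported secondary endpoints, and state whether each is analysed as an amount or as yes/no. Discharge prescription stays separate.
3. State that an overall opioid-sparing conclusion rests on the total and not on the intraoperative result alone.

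Separately, Sections 5.6 and 6.2.2.1 to 6.2.2.3 must be reconciled on opioid use by arm, and the report should acknowledge that the anesthesia team is not blinded.

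The cost is protocol and SAP wording, one conversion table, one more secondary analysis, and collection of PACU and ward opioid amounts to POD1 from the medical record. Section 5.5 describes only the intraoperative medication record, so the postoperative collection needs to be written in. The downside is that a reduction confined to surgery no longer supports the overall claim.

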3.2 Primary Study Endpoints

This study will evaluate the efficacy of magnesium sulfate on decreasing esophageal spasm-associated pain as measured by subjective pain scores and the esophageal symptoms questionnaire score.

CONFIDENTIAL

This document is confidential and the property of Stanford University School of Medicine.

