will receive dexamethasone and ondansetron in the aforementioned doses. After surgery, patients will be admitted to the postanesthesia care unit, where opioids (fentanyl and hydromorphone) and antiemetics (anesthesia team's discretion) will be available for further pain and nausea management.

6.3 All study participants will repeat the ESQ in the PACU when the nursing team deems the patient's recovery appropriate enough to participate.

6.4 Postoperative Day 1

6.4.1 The ESQ and serum calcium/magnesium levels will be reobtained in the morning of POD1.

7 Statistical Plan

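### The 24-hour ESQ score is compared between arms without using the preoperative ESQ score that the trial already collects

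*Combined protocol and SAP*

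**What the plan says.** **Endpoint.** Section 3.3 includes among the secondary endpoints "decreasing postoperative pain as measured by the esophageal symptoms questionnaire score at 24 hours", and section 2 has a matching secondary objective. Section 3.2 also brings the ESQ into the primary endpoint, where pain is assessed "as measured by subjective pain scores and the esophageal symptoms questionnaire score".

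**Data collected.** Under section 6.2.1 all enrolled patients, in preoperative holding, "complete the esophageal symptoms questionnaire (ESQ), a validated survey to assess symptoms of dysphagia, globus, and reflux". Section 6.3 adds: "All study participants will repeat the ESQ in the PACU". Section 6.4.1 adds: "The ESQ and serum calcium/magnesium levels will be reobtained in the morning of POD1". The last of these is the 24-hour measure.

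**Analysis.** The Study Summary (Statistical Methodology) allows categorical tests (chi-square or Fisher) and also names the "Mann-Whitney U test to compare secondary outcomes (intraoperative opioid usage, postoperative opioid usage, pain at 24 hours, esophageal symptoms questionnaire results". Section 7.2 does not name the ESQ. It reaches the score only through the rule beginning "Continuous variables will be compared using the", which goes on to specify the Mann-Whitney U test. No section mentions a covariate, a regression model, change from baseline or stratification by the preoperative ESQ.

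**Significance level.** Section 7.2 uses P < 0.05 generally. It then says that comparisons of postoperative pain at 0 h and 24 h will be "performed using an adjusted significance level of 0.0125 (0.05/4", without naming the four tests.

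**The concern.** The preoperative ESQ is on the same scale as the endpoint and is recorded before the study drug is given, so it is a natural covariate. Left out of the analysis, differences between patients in their symptoms before surgery remain in the error term. If preoperative and postoperative scores are moderately correlated, the trial could miss an ESQ difference that the same patients and the same forms would have shown. Adjustment would also guard against a chance imbalance in preoperative symptoms, which is possible in a trial of 100.

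This applies to the ESQ outcomes only. The numeric pain score has no scheduled preoperative measurement.

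A lesser point concerns the 0.0125 level. One pain measure at two times makes two tests, not four. Pain score and ESQ, each at two times, would make four, but the plan does not say so. A reader therefore cannot tell whether an ESQ comparison is judged at 0.0125 or at 0.05.

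**Working it through.** **The plan's own figure.** The documents give no power or sample size for the ESQ. The only calculation (section 7.1) is for the binary pain outcome: 60% incidence, a decrease of 30% (read here as absolute, to 30%), two-sided alpha 0.05 and power 80%.
- Average-proportion formula: (1.960 + 0.842)² × 2 × 0.45 × 0.55 / 0.30² = 43.2, so 44 per arm. The usual pooled formula gives 42.
- The stated 45 is close to these and slightly conservative (82.8% power). Dropout: 45 / 0.90 = 50, as stated.

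So 45 analysed per arm is used below.

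**Assumptions that the documents do not supply.** These are the correlation rho between preoperative and later ESQ scores, the size of an ESQ effect, and the shape of the score distribution. Rho is varied from 0 to 0.7, and scores are taken as normal.

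**Detectable difference (80% power, two-sided 0.05).**
- Unadjusted t test: 2.802 × √(2/45) = 0.59 SD.
- Mann-Whitney, with efficiency 3/π under normality: 0.591 / √(3/π) = 0.60 SD.
- Linear adjustment for the preoperative score multiplies the variance by 1 − rho². The cut is 1%, 9%, 25% and 49% at rho 0.1, 0.3, 0.5 and 0.7.
- The detectable difference with adjustment is 0.591 × √(1 − rho²): 0.56, 0.51 and 0.42 SD at rho 0.3, 0.5 and 0.7.
- Relative to an unadjusted t test, this is like having 45 / (1 − rho²) patients per arm: about 49, 60 and 88.

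**Simulated power.** The true shift was set at 0.604 SD, so that Mann-Whitney has about 80% power at 0.05. Each setting used 20,000 simulated trials (simulation error about 0.3 points). Rank ANCOVA follows Quade: regress the ranks of the outcome on the ranks of the preoperative score, then compare residuals between arms.

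| rho | Mann-Whitney, 0.05 | Rank ANCOVA, 0.05 | Mann-Whitney, 0.0125 | Rank ANCOVA, 0.0125 |
|---|---|---|---|---|
| 0 | 78.9% | 78.5% | not run | not run |
| 0.1 | 79.1% | 79.0% | 59.8% | 60.6% |
| 0.3 | 79.2% | 82.2% | 59.7% | 64.7% |
| 0.5 | 79.4% | 88.2% | 59.7% | 73.8% |
| 0.7 | 78.8% | 96.3% | 59.1% | 88.8% |

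The type I error of rank ANCOVA at nominal 0.05 was 0.050, 0.053 and 0.051 at rho 0, 0.5 and 0.7.

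**A smaller true effect.** At 0.5 SD and level 0.05, the normal approximation gives 64% power for Mann-Whitney. Linear ANCOVA has 70%, 78% and 91% at rho 0.3, 0.5 and 0.7.

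**Test family.**
- Four tests at 0.0125: 4 × 0.0125 = 0.05.
- Two tests at 0.0125: 2 × 0.0125 = 0.025, stricter than needed.
- Four tests at 0.025: 4 × 0.025 = 0.10, too lenient.

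Which level applies also matters for power. Mann-Whitney falls from about 79% at 0.05 to about 60% at 0.0125.

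**The case against.** The unadjusted Mann-Whitney test is valid and conventional for a secondary score in a single-center trial of 100, and the plan never promises adjustment. The benefit rests on an unknown rho, and there is reason to expect a low one. The preoperative ESQ measures disease symptoms, surgery for that disease comes between the measurements, and the PACU form is completed during recovery from anesthesia. At rho 0.1 there is no gain at 0.05, and at 0.3 it is 3 points. The 0.60 SD shift was chosen to give Mann-Whitney about 80% power; it is not a trial assumption.

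All of that stands as a limit on the size of the gain. It does not remove the point, because the trade is one-sided: under half a point lost if rho is zero, against about 9 points gained at rho 0.5.

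It can also be said that the plan should first settle what the ESQ outcome is. The summary allows categorical tests for ESQ results, section 7.2 never names the ESQ, and section 3.2 places it in the primary endpoint while section 7.2 makes the primary outcome a binary incidence. Those ambiguities are real and should be resolved in the same edit. They do not block the change, since section 3.3 words the endpoint as a score and a rank-based covariate analysis suits a score. Finally, whether the ESQ falls under the 0.0125 sentence is itself an inference, so that part is a request for clarification only.

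**Conclusion.** The point holds. The plan collects a preoperative ESQ from every enrolled patient and gives it no role in analysing the ESQ endpoint. The consequence is a possible loss of precision. There is no bias, because allocation is randomized, and the primary chi-square test and the sample size do not change.

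With 45 analysed per arm, normal scores and a shift of about 0.60 SD, rank ANCOVA changes power at 0.05 by about 0, +3, +9 and +17 points at rho 0.1, 0.3, 0.5 and 0.7. At 0.0125 the gains are about 1, 5, 14 and 30 points. The gain is therefore negligible to small unless rho is about 0.5 or higher, and the documents do not say what rho is. The change is worth making because it costs almost nothing, but it is an improvement to a secondary analysis and not a correction of an invalid one. The unlisted family behind 0.0125 is a separate, smaller gap.

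**What to change.** Add to section 7.2 a statement to this effect: *ESQ scores in the PACU and on POD1 will each be compared between arms by rank ANCOVA with the preoperative ESQ score as covariate; the unadjusted Mann-Whitney U test is a sensitivity analysis.* Change the Study Summary to match. If an effect estimate is wanted, a proportional-odds model with arm and preoperative ESQ gives an odds ratio with a 95% CI. In that case, state that the rank ANCOVA p-value governs the conclusion, since the two models can disagree. Keep Mann-Whitney for the numeric pain score.

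In the Bonferroni sentence, list the tests and match the divisor to the list. Keep 0.0125 if pain score and ESQ are each tested at 0 h and 24 h; use 0.025 only if exactly two tests are listed.

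The cost is some SAP wording, a few lines of R and one covariate, plus the proportional-odds assumption if the odds ratio is reported. No new data, visits or patients are needed. The change must be fixed before anyone sees unblinded data, because adding it later would look like a data-driven choice.
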